9.5 Protocol Compliance

The PI will conduct the trial in compliance with the protocol agreed to by the sponsor. The investigator will not implement any deviation from, or changes to, the protocol without agreement, prior review, and documented approval by the sponsor and the IRB that granted original approval for the study. The DSMB will be made aware of all protocol revisions (other than administrative) and will review any changes to the protocol that involve DSMB oversight or involve changes to the study's data and safety monitoring plan. However, the investigator may implement a deviation from, or change in, the protocol to eliminate an immediate hazard(s) to subjects without prior IRB or sponsor approval, or when the change(s) involves only logistical or administrative aspects of the trial (i.e., change of telephone number[s]). In the event of a medical emergency, the PI will perform any medical procedures that are deemed medically appropriate.

As soon as possible, the implemented deviation or change, the reasons for it, and, if appropriate, the proposed protocol amendment(s) should be submitted to the Sponsor, IRB, DSMB, and the regulatory authorities.

9.6 Clinical Investigator's Brochure

Investigators will receive the current versions of the Clinical Investigator's Brochure for the live attenuated Zika vaccine rZIKV/D4Δ30-713, which comprehensively describes all the available preclinical experience with the experimental vaccine. If relevant new information becomes available during the course of the trial, the investigators will receive a revised brochure or an amendment to the current version.

9.7 Study Monitoring

As per ICH-GCP 5.18 and FDA 21 CFR 312.50, clinical protocols are required to be adequately monitored by the sponsor. This study monitoring will be conducted according to the "NIAID Intramural Clinical Monitoring Guidelines." The sponsor will monitor all aspects of the study,

with respect to current GCP, for compliance with applicable government regulations. Prior to the start of the study, the investigator will be informed of the frequency of monitoring visits and will be given reasonable notification prior to each visit. The objectives of a monitoring visit will be to verify the prompt and accurate recording of all monitored data points, and prompt reporting of SAEs; to check the availability of signed informed consent forms and documentation of the informed consent process for each monitored subject; to compare CRIMSON reports and line listings with source data for completeness and accuracy; and to help ensure investigators are in compliance with the protocol. The monitors will also inspect the clinical site regulatory files to ensure that regulatory requirements (Office for Human Research Protections, FDA) and applicable guidelines (ICH GCP) are being followed. During the monitoring visit, the investigator (and/or designee) and other study personnel should be available to discuss the study. Study documents must be available for review throughout the course of the study. The sponsor will retain original copies of Form FDA 1572 and copies of other study documents as deemed necessary.

The investigator (and/or designee) will make study documents (e.g., consent forms, CRIMSON, and pertinent hospital or clinical records) readily available for inspection by the local IRB, the FDA, the site monitors, and NIAID staff for confirmation of the study data.

A specific protocol monitoring plan will be discussed with the PI and study staff prior to enrollment. The plan will outline the frequency of monitoring visits based on such factors as study enrollment, data collection status, and regulatory obligations.

10 STATISTICAL CONSIDERATIONS

10.1 General Design

The goal of the Phase 1 vaccine trial is to determine the safety and immunogenicity of rZIKV/D4Δ30-713, a live attenuated Zika vaccine candidate in healthy human subjects. The purpose of the Phase 1 trial is to evaluate the reactogenicity, immune response to Zika vaccine and the persistence of antibody following subcutaneous administration of a single dose of rZIKV/D4Δ30-713.

10.2 Statistical Methods

This study, like other Phase 1 studies, is exploratory rather than confirmatory; its purpose is to estimate event frequencies and patterns of immune responses rather than to test formal statistical hypotheses. Descriptive approaches will be used to meet the protocol objectives as stated in Section 3 of this protocol, as outlined below. Results will be presented in tabular format, as well as graphically where appropriate.

Primary Objective 1: Determine the safety and reactogenicity of a single dose of the LA Zika vaccine rZIKV/D4Δ30-713, as assessed by the frequency of adverse events (AEs) and adverse reactions (AR) as defined as vaccine-related adverse events (AE)s, graded by severity.

The frequency of immediate, systemic, and local AEs and ARs following vaccination will be summarized. AEs and ARs will be displayed in tabular format, with line listings of individual clinical and laboratory AEs and ARs classified as immediate, systemic, and

local events and AEs and ARS will be summarized by severity and relationship to vaccine by individuals and each group (rZIKV/D4Δ30-713 and placebo).

Primary Objective 2: To determine the immunogenicity of a single dose of rZIKV/D4Δ30-713, as assessed by:

- Determination of the serum plaque reduction neutralization titer 50% (PRNT₅₀) to ZIKV for each subject at Study Day 28, 56, and 90 post-inoculation. Seroconversion will be defined as achieving a PRNT₅₀ ≥ 1:10 at any time-point through Study Day 90 (Day 28, 56, or 90). The peak PRNT₅₀ to ZIKV through Study Day 90 will be calculated for each subject included in the per-protocol an intent-to-treat analysis and the geometric mean peak titer for vaccinated subjects will be calculated.

Secondary Objective 1: Assess the frequency, quantity, and duration of viremia (virus in the blood) induced by a single dose of the rZIKV/D4Δ30-713 vaccine. The mean peak viremia, mean day of onset of viremia, and mean duration of viremia will be calculated. Viremia will be detected by culture (infectious virus) and by RT-PCR.

Secondary Objective 2: Determine the number of vaccinees infected with rZIKV/D4Δ30-713. Infection is defined as recovery of infectious vaccine virus from the blood, serum or urine of a subject and/or by seroconversion to ZIKV. Seroconversion will be defined as achieving a PRNT₅₀ ≥ 1:10 by Study Day 90 post-vaccination.

Secondary Objective 3: Evaluate the immunogenicity of rZIKV/D4Δ30-713 in flavivirus-naïve subjects as assessed by the PRNT₅₀ to ZIKV, for each subject at Study Day 28, 56, and 90 post-administration of LA Zika vaccine.

Secondary Objective 4: Determine the durability of antibody response 26 weeks after vaccination.

Secondary Objective 5: Determine the quantity and duration of ZIKV presence as determined by:

- The peak virus titer in the blood and the duration of viremia induced by the LA Zika vaccine as determined by RT-PCR and virus culture
- The quantity and duration of possible Zika vaccine shedding in urine determined by RT-PCR and virus culture
- The quantity and duration of possible Zika vaccine shedding in vaginal secretions determined by RT-PCR and virus culture
- The quantity and duration of possible Zika vaccine shedding in semen determined by RT-PCR and virus culture

Exploratory Objective 1: To evaluate the phenotype of peripheral blood mononuclear cells (PBMCs) at primary infection with the rZIKV/D4Δ30-713 vaccine.

Exploratory Objective 2: To evaluate the cellular immune response to primary infection with the rZIKV/D4Δ30-713 vaccine.

Exploratory Objective 3: To evaluate the innate immune response to primary infection with the rZIKV/D4Δ30-713 vaccine.

Exploratory Objective 4: To evaluate B and T cell memory responses following primary infection with rZIKV/D4Δ30-713 vaccine.

Exploratory Objective 5: To evaluate the antibody response in saliva to infection with rZIKV/D4Δ30-713 as a possible diagnostic tool. This will be done in a subset of subjects (those enrolled at the Center for Immunization Research [CIR]).

10.3 Safety Endpoint

The primary safety endpoint is the frequency of rZIKV/D4Δ30-713-related AEs, as classified by both severity and seriousness, through active and passive surveillance. Separate assessments of systemic and local reactions will be performed.

10.4 Immunogenicity

Zika virus neutralizing antibody titers will be measured on study day 0 (prior to inoculation) and Study Days 28, 56, 90, and 180 following vaccination with rZIKV/D4Δ30-713. Seropositivity to ZIKV will be defined as a PRNT₅₀ of $\geq 1:10$. Seroconversion will be defined as a PRNT₅₀ of $\geq 1:10$ to ZIKV by study day 90. Seroconversion will be defined as a PRNT₅₀ of $\geq 1:10$ to ZIKV or following administration of rZIKV/D4Δ30-713.

10.5 Per Protocol Analysis

10.5.1 Safety Data

Subjects who have completed ≥ 5 visits through Study Day 28 will be included in the per-protocol analysis of the AE / adverse reaction data. All SAEs and AEs of special interest will be included in the per-protocol analysis.

10.5.2 Virology

Subjects who have completed ≥ 5 visits through Study Day 28 will be included in the per-protocol analysis of the virology data.

10.5.3 Immunogenicity Data

Subjects who have completed at least 2 of the Study Day 28, Study Day 56, and Study Day 90 visits will be included in the per-protocol analysis of the immunogenicity data.

10.6 Intent-to-treat analysis

10.6.1 Safety Data

All subjects, regardless of the number visits that they missed, will be included in the safety analysis. This will include subjects who were replaced.

10.6.2 Virology

All subjects, with the exception of those who were replaced, regardless of the number visits that they missed, will be included in the virology analysis.

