5.3 Subject Withdrawal and Termination Criteria

A subject will not be considered to have completed the trial if any of the following reasons apply. However, any subject who has received vaccine or placebo will be encouraged to remain in the study for periodic safety evaluations for the duration of the study at the discretion of the investigator. Subjects who have been terminated from the study or withdrawn from the study prior to study day 28 may be replaced to ensure sufficient safety data for rZIKV/D4Δ30-713 are collected.

1. ***Research terminated by sponsor or investigator*** – applies if the entire study is terminated by the sponsor or investigator for any reason.
2. ***Withdrawal of consent*** – applies to a subject who withdraws consent to participate in the study for any reason.
3. ***Noncompliant with protocol*** – applies to a subject who does not comply or is not able to comply with protocol-specific visits or evaluations on a consistent basis such that adequate follow-up is not possible, and the subject's safety and the study data's integrity would be compromised by continuing in the trial.
4. ***Withdrawn by PI*** – may occur if the investigator believes that it is in the best interest of the subject to be withdrawn from the study.
5. ***Other*** – a category used when previous categories do not apply and requires an explanation.

5.4 Special Situations:

5.4.1 *Pregnancy:*

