7.5.2 Notification of Staff of COVID-19-like symptoms

Subjects will be asked to call or otherwise contact study staff should they experience any COVID-19 symptoms. In addition, at each visit, volunteers will be asked whether or not they have experienced any COVID-19 symptoms (per facility guidelines) or if they have had an exposure to someone with COVID-19 prior to coming into the clinic. If the volunteer reports symptoms consistent with COVID-19 and they are already enrolled in the study, an NP or mid-turbinate swab will be collected and tested for COVID-19 on site or at a local laboratory at any time. The volunteer will not come into the clinic until the result is confirmed to be negative. Should a volunteer test positive for SARS-CoV-2 at any point during the study, the volunteer will be asked to quarantine according to current CDC guidelines. We will review current CDC guidelines with the volunteer. We will defer all in-person visits until after the volunteer has completed their quarantine or see them in a COVID-19 positive research space if it is available. If they test positive for SARS-CoV-2 during the first 21-days post-vaccination, scheduled follow-up visits will be done as telehealth visits or in a COVID-19 positive research space.

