10.6.3 Immunogenicity Data

All subjects, with the exception of those subjects who were replaced, who have had at least one specimen collected at an immunogenicity time-point, regardless of the number visits that they missed, will be included in the immunogenicity analysis.

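### The intent-to-treat virology and immunogenicity sets drop dosed subjects who were replaced, and per-protocol virology counts visits rather than results, so viremia and shedding frequencies can be biased

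*Combined protocol and SAP*

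**What the plan says.** Section 5.3 sets the replacement rule: "Subjects who have been terminated from the study or withdrawn from the study prior to study day 28 may be replaced". Its stated purpose is to secure enough safety data. Section 4.1 counts a subject as enrolled only once test article has been given, so a replaced subject has been dosed.

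The intent-to-treat sets then treat these subjects in two ways:
- Safety (10.6.1): "This will include subjects who were replaced".
- Virology (10.6.2): "All subjects, with the exception of those who were replaced, regardless of the number visits that they missed".
- Immunogenicity (10.6.3): "All subjects, with the exception of those subjects who were replaced, who have had at least one specimen collected at an immunogenicity time-point".

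Per-protocol virology (10.5.2) has one criterion: "Subjects who have completed ≥ 5 visits through Study Day 28 will be included in the per-protocol analysis of the virology data". It sets no condition on samples or results and does not exclude replaced subjects.

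Under 7.4.1, blood and urine virology is unconditional after dosing on Days 4, 6, 8, 10, 12, 14 and 16. At Days 21 and 28 it is run only if the preceding time-point was positive. Semen and vaginal samples are taken at baseline, on Days 8 and 16, and then from Day 28, where testing is again conditional. For a subject who tests positive for SARS-CoV-2 in the first 21 days, 7.5.2 says "scheduled follow-up visits will be done as telehealth visits or in a COVID-19 positive research space".

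**The concern.** An intent-to-treat set should not depend on what happens after dosing. Here membership depends on early departure and on a staff decision to replace, and either could be related to the vaccine. Virology already obtained from such a subject is left out of the analysis meant to be the most inclusive one.

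The per-protocol rule has a different weakness. It is meant to select adequately observed subjects, but attendance at Days 21 and 28 counts towards the threshold without normally producing a virology result.

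At stake are the secondary frequencies of viremia and of shedding by fluid, in cohorts of 20 vaccinees. The same exclusion in 10.6.3 touches the primary immunogenicity endpoint. Section 10.2 describes the study as estimating frequencies rather than testing hypotheses, so the choice of denominator is a central part of the analysis.

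**Working it through.** **Design figure.** 2 cohorts × 4 blocks × (5 + 2) = 56, that is 40 vaccine and 16 placebo, which agrees with 4.1.2. The plan gives no expected viremia rate and no power or precision for virology, so there is no further figure to reproduce.

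**Nesting.** Take a subject who attends Days 4 to 16, leaves on Day 20 and is replaced.
- Visits completed: 7, which is at least 5, so the subject is in per-protocol virology (10.5.2).
- Replaced, so not in intent-to-treat virology (10.6.2).

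The per-protocol set can therefore contain someone whom the intent-to-treat set lacks. This needs no assumption about bias.

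**Visits against samples.** Visits through Day 28 are Days 4, 6, 8, 10, 12, 14, 16, 21 and 28: nine, or ten with Day 0. The plan does not say whether Day 0 counts.
- Fewest unconditional post-dose blood samples with five visits: 5 − 2 = 3 (for example Days 4, 6, 8, 21, 28). If Day 0 counts: 5 − 3 = 2 (Days 0, 4, 6, 21, 28).
- Both patterns stop unconditional sampling by Day 8. The mean onset days of viremia in Table 6, for related vaccines, run from 9.2 to 15.3.
- Five-visit patterns with neither Day 8 nor Day 16: C(7,5)/C(9,5) = 21/126 = 17%, or C(8,5)/C(10,5) = 56/252 = 22% with Day 0. These count possible patterns and are not probabilities.

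For any one subject, being ever positive can only stay the same or be missed as samples are lost. Sparse sampling therefore acts in one direction, downward.

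**Replacement.** Let x of the 20 retained vaccinees be positive, and y of k replaced vaccinees. The rule reports x/20, while all dosed gives (x + y)/(20 + k). The documents give no k, so k = 1 to 3 per cohort is an assumption. Intervals are exact (Clopper-Pearson) 95%.

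| Retained | Replaced, positive/total | All dosed |
|---|---|---|
| 0/20 = 0% (0 to 16.8%) | 1/1 | 1/21 = 4.8% (0.1 to 23.8%) |
| 0/20 | 2/2 | 2/22 = 9.1% (1.1 to 29.2%) |
| 0/20 | 3/3 | 3/23 = 13.0% (2.8 to 33.6%) |
| 0/20 | 0/1, 0/2, 0/3 | 0%, upper limit 16.1%, 15.4%, 14.8% |
| 4/20 = 20% | 0/3 | 4/23 = 17.4% |
| 4/20 = 20% | 3/3 | 7/23 = 30.4% |

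The shift can go either way, and is nil with k = 0.

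**Untested subjects.** The plan does not say how they are handled. If 2 of 20 had no result, 4 positives could be reported as 4/20 = 20% or 4/18 = 22.2%, and could be as high as 6/20 = 30%. With no positives the upper limit is 16.8% for n = 20 and 18.5% for n = 18.

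**A related gap.** In 7.4.1, testing of Day 28 semen and vaginal samples depends on a Day 21 finding, but no such sample is scheduled on Day 21. These passages must be reconciled.

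**The case against.** The study is exploratory and descriptive, virology is secondary, and 8.5.1.2 halts enrollment on any detection in semen or vaginal secretions whatever the analysis set. All of that stands and limits the consequence. It does not correct a reported frequency, and the halting rule does not cover blood or urine.

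Replacement may never happen. Section 2.3.2 reports 20 recipients of the lower dose, and Tables 7 and 8 show n = 20, which suggests that no vaccinee in Cohort 1 was dosed and then replaced. For vaccinees, the replacement issue then matters mainly for Cohort 2. The effect on 10.6.3 is probably small too, since few subjects leaving before Day 28 will have a post-dose titer.

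Several stronger readings are tempting, and the documents do not support them:
- That frequencies are pushed toward none overall. The replacement effect has no known direction.
- That unsampled subjects are scored as not viremic. The plan is silent.
- That the Day 20 leaver's results are lost altogether. They remain in per-protocol virology.
- That telehealth contacts count as completed visits. Nothing says whether they do, and an in-person alternative is offered.
- That one subject moves any rate by 1/20 = 5 points. Semen and vaginal denominators are split by sex, in proportions not stated, and are smaller than 20.
- That missed viremia must lower the infection rate. Infection can also be shown by seroconversion through Day 90.

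**Conclusion.** The point holds as a defect in how the analysis sets are defined. The intent-to-treat virology and immunogenicity sets are not intent-to-treat, they conflict with the safety set, and the virology sets are not nested. The per-protocol virology rule does not secure the results it is meant to rest on: three of seven blood samples suffice (two if Day 0 counts), and no post-dose semen or vaginal result is required.

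The supportable conclusion is that frequencies can be biased, not that they are. The replacement effect could be zero. In the illustration it is 4.8 points for one positive replaced vaccinee against none among 20, and it rests on assumed replacement counts. The sampling effect on any viremia can only be downward, and its size depends on attendance, which the plan cannot tell us. Table 6 onset days come from other vaccines and are only a guide. The change should be made before the final analysis, but it does not put the trial's conduct in question.

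**What to change.** Revise 10.5.2, 10.6.2 and 10.6.3 as follows:
- **Intent-to-treat virology:** for each fluid, every dosed subject with at least one post-dose result for that fluid, replaced or not.
- **Intent-to-treat immunogenicity:** every dosed subject with at least one serum titer after Day 0, replaced or not. Because 10.4 lists Day 0 among the titer days, the present wording could admit a subject with a baseline specimen only.
- **Per-protocol virology:** based on results obtained. For blood and urine, at least 5 of the 7 Day 4 to 16 results. For semen or vaginal secretions, the Day 8 and/or Day 16 result.
- **Reporting:** number positive over number tested, by fluid and time-point, with semen and vaginal denominators by sex. Do not count untested subjects as negative. Show replaced subjects' results.

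Five of seven results can still end at Day 12, and a single result can admit a subject to the intent-to-treat set, so the time-point table is needed to show how complete the sampling was. The Day 21 and Day 28 conditions for semen and vaginal testing should be reconciled in the same edit.

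The cost is a short text amendment and one added table. No new visits, samples or assays are needed.

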10.6.3 Immunogenicity Data

All subjects, with the exception of those subjects who were replaced, who have had at least one specimen collected at an immunogenicity time-point, regardless of the number visits that they missed, will be included in the immunogenicity analysis.

11 PROTECTION OF HUMAN SUBJECTS

11.1 Institutional Review Boards

The PI will be responsible for obtaining IRB approval for the study. Before the start of the study, the appropriate documents (including, but not limited to, the protocol, Investigator's Brochure, Informed Consent Form, information sheets, and advertisements) will be submitted to the IRB for approval. A copy of the study approval (including approval of the informed consent form) is to be maintained in the investigator study document binder and a copy will be supplied to the sponsor. During the study, the investigator is responsible for providing the IRB with all documents subject to review (e.g., protocol amendments, informed consent form updates, advertisements, and any written information that may be provided to the subject). Annual reports on the progress of the study will be made to the IRB by the investigator in accordance with IRB guidelines and government regulations.

11.2 Data Safety Monitoring Board

The Sponsor has convened a DSMB to review this study at regular intervals. The DSMB is comprised of individuals with expertise in clinical flavivirus vaccine studies, statistics, clinical trials, and infectious diseases. The study team will provide the DSMB with all requested data/materials they have requested for review at regular intervals determined by the DSMB. If a Halting Rule is triggered, the DSMB will review the event and decide, in collaboration with the PI and Sponsor, whether or not the study should continue (Section 8.5).

11.3 Informed Consent

In obtaining and documenting informed consent, the investigator and study staff must comply with the applicable regulatory requirements, GCP guidelines, and ethical principles. The written informed consent form must be approved by the IRB prior to its use. The subject may withdraw consent at any time during the course of the trial. A copy of the informed consent document will be given to the subject for his or her records. The rights and welfare of the subjects will be protected by emphasizing to them that the quality of their medical care will not be adversely affected if they decline to participate in this study.

